5.2.1 Safety Follow-Up Visit (Week 25±7 days)

Once a patient has completed treatment with 6 doses of Radium-223, or the patient is prematurely discontinued from treatment for any reason specified in Section 5.6 Removing Patients from the Protocol, the patient will complete a safety follow-up visit including the following assessments:

- Physical exam
- ECOG performance status
- Vital signs [body temperature, blood pressure, pulse, respiratory rate, weight]
- ECG (as clinically indicated – not required at every visit)
- Pain scale (BPI Short Form using a PRO instrument)
- Fatigue scale (BFI item using a PRO instrument)
- Analgesic diary
- Lab tests [hematology, serum biochemistry, PSA]
- Adverse events and concomitant medications will be monitored continuously throughout the study

For the pain and fatigue scale, data will be entered by the subject daily during the 7 day reporting period prior to their safety visit. Subjects will also update their analgesic dairy during this 7 day period as well.

5.3 Follow-Up

- Patients will be evaluated every 3 months (+/- 1 week) until 6 months after the safety follow-up visit for a total of 2 visits or until initiation of another therapy. The following assessments will be performed at these visits:
 - ECOG Performance Status
 - Pain scale (BPI Short Form using a PRO instrument)
 - Fatigue scale (BFI item using a PRO instrument)
 - Analgesic diary
 - Lab tests [hematology, serum biochemistry, PSA]
 - Imaging Assessments: Bone scan, FDG PET (FDG will be done in consenting patients and is considered optional) , CT scan or MRI of the abdomen and pelvis and CT scan of the chest or Chest X-ray

The follow-up visit should be calculated from the date of the safety follow-up visit for Radium-223. For the pain and fatigue scale, data will be entered by the subject daily during the 7 day reporting period prior to their follow-up visit. Subjects will also update their analgesic dairy during this 7 day period as well.

Radium-223

MSKCC

5.4 Clinical and laboratory assessments

PCCTC LOI: c13-124

IRB#: 14-098 A (5)

Medical History

Medical history findings (i.e. previous diagnoses, diseases or surgeries) meeting all criteria listed below will be collected:

- Not pertaining to the study indication
- Start before signing of the informed consent
- Considered relevant to the study

ECOG Performance Status

Performance status will be assessed using ECOG performance status criteria. See Appendix A: Performance Status Criteria for a KPS-ECOG conversion chart.

Vital Signs

Vital signs include body temperature, blood pressure, respiratory rate, pulse, weight and height. Height will be performed at screening only.

Physical Exam

The physical exam will include a full review of the body systems.

Electrocardiogram (ECG)

A 12-lead ECG will be recorded at screening and whenever an Investigator determines it clinically indicated throughout the treatment period.

Adverse Event Monitoring

Patients will be closely monitored throughout the study for adverse events, at least every four weeks. Adverse events and other symptoms will be graded according to NCI CTCAE v4.0. Adverse events will be monitored from the first dose of *Radium-223* through 4 weeks following the last administration or until all study drug-related toxicities resolve, stabilize, return to baseline or are deemed irreversible, whichever is longer.

Laboratory Test Assessments

Hematology: white blood cells count (WBC), red blood cell count (RBC), hemoglobin (HGB), hematocrit (HCT), , platelet count (UNVPLT), neutrophils (NEUTP), lymphocytes (LYMP), Serum Biochemistry: calcium (CA), albumin (ALB), total protein (TP), sodium (NA), potassium (K), chloride (CL), blood urea nitrogen (BUN), creatinine (CREAT), alkaline phosphatase (ALK), alanine transaminase (ALT), aspartate transaminase (AST), total bilirubin (TBILI), lactate dehydrogenase (LDH), gamma-glutamyl transpeptidase (GGT), phosphate (PHOS), magnesium (MG), glucose (GLU), carbon dioxide (CO2)

Serum PSA (PSA)

Radium-223

MSKCC

PCCTC LOI: c13-124

IRB#: 14-098 A (5)

Bone markers: bone specific alkaline phosphatase (BAP), serum N-telopeptide (SNTX), serum C-telopeptide (SCTX), procollagen type I N-terminal propeptide (PINP)

Testosterone level (*TEST*)

BPI short form (pain scale)

A Patient Reported Outcome (PRO) instrument will be performed by patients to assess level of pain which includes a change in BPI worst pain item from baseline (See Appendix I for instructions). BPI functional interference index (general activity, sleep) will be collected.

Measure of fatigue

Patient Reported Outcome (PRO) instrument will be performed by patients to assess fatigue using the Brief Fatigue Inventory (BFI). Patients will be asked to "Please rate your fatigue (weariness, tiredness) by circling the one number that best describes your WORST level of fatigue during the past 24 hours," with rating via an 11-point numerical rating scale anchored by zero demarking "No fatigue" and 10 demarking fatigue "As bad as you can imagine."

Analgesic diary

Records daily intake of analgesic medications. A question confirming that subject's pain medication diary has been completed is included in the PRO instrument.

Tumor Assessment and Bone Scan

Radiographic disease assessment will be obtained every 12 weeks during active treatment and every 3 months during the long-term follow-up portion using PCWG2 criteria as described in Section 8.3 Therapeutic Response.

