^b Imaging assessments will be performed every 12 weeks \pm 1 week. Bone scan, FDG PET (FDG will be done in consenting patients and is considered optional), CT scan or MRI of the abdomen and pelvis and CT scan of the chest or Chest X-ray

^c Hematology: White blood cells count (WBC), red blood cell count (RBC), hemoglobin (HGB), hematocrit (HCT), platelet count (UNVPLT), neutrophils (NEUTP), lymphocytes (LYMP), monocytes (MONP), eosinophils (EOSP), basophils (BASOP)

^d Serum biochemistry: calcium (CA), albumin (ALB), total protein (TP), sodium (NA), potassium (K), chloride (CL), blood urea nitrogen (BUN), creatinine (CREAT), alkaline phosphatase (ALK), alanine transaminase (ALT), aspartate transaminase (AST), total bilirubin (TBILI), lactate

dehydrogenase (LDH), gamma-glutamyl transpeptidase (GGT), phosphate (PHOS), magnesium (MG), glucose (GLU), carbon dioxide (CO2)

- ^e Subjects should be followed up every 3 months following the safety follow-up visit for a total of 2 visits or until initiation of another therapy and be assessed for any potential long term toxicity as well as key efficacy parameters
 - ^f Subjects will indicate their daily pain score for 7 days during the 28 day screening period to establish that their average baseline pain score is ≥ 3 as measured for 4 of 7 days.
 - ^g During the follow-up period, subjects will answer questions on the BPI and BFI as well as enter information on their analgesic dairy for at least 4 of 7 days prior to their scheduled follow up visit
 - ^h Subjects will update their analgesic dairy daily during the run-in period and daily during the pain assessment periods throughout the trial
-

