The quantification of radium-223 radioactivity in Xofigo (radium-223 dichloride; BAY 88-8223) is based on the primary standardization performed by the US NIST. National Institute of Standards and Technology prepares the standard reference material (SRM) using an official dial setting (primary standardization) as published.¹⁶ The NIST SRM is used to calibrate the instruments in production and quality control for both the drug substance and drug product. Additionally, the NIST SRM is used to prepare the NIST traceable Ra-223 reference materials which are then sent to the end-users (e.g., nuclear medicine laboratory physicians or technicians) for dial-setting of their dose calibrators, to allow verification of the patient dose. In 2014, NIST performed a re-assessment of the primary standardization based on preliminary information suggesting a potential discrepancy of approximately 8-10% between the published NIST primary standardization¹⁶ and results obtained by other national metrology institutes (United Kingdom, Germany, Japan). After completion of the re-assessment, NIST reported their findings¹⁷ and had issued a revised NIST SRM in 2015. The discrepancy in the NIST standardization was determined to be -9.5% between activity values obtained using the old reference standard relative to the new primary standardization. Consequently the current numerical values need to be corrected by approx. + 10.5%.

The change in the numerical description of the patient's dose, product strength and labeled vial activity does not impact the safety or efficacy of Xofigo. The change in the NIST radium-223 standard has no impact on subjects; dose subjects are receiving, and will continue to receive.

Subjects will receive the same actual dose and volume that was studied in Study 15245 (BC1-06 dosimetry study) and is associated with the proven safety and efficacy of radium-223 dichloride, though the stated nominal radiation dose received has been updated to reflect the new standard.

7. **ADVERSE EVENTS**

7.1 **Definitions**

7.1.1 *Adverse Event (AE)*

Radium-223

MSKCC

PCCTC LOI: c13-124

IRB#: 14-098 A (5)

An adverse event is any untoward medical occurrence in a research patient during a clinical study or within 4 weeks post treatment, regardless of causality. This includes adverse clinical or laboratory findings, any adverse drug reaction (ADR), and an illness with onset during the study, or an exacerbation of preexisting illness or condition.

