8.2 Secondary endpoints

- Bone-ALP response will be described as:
 - Percentage of change from baseline to 12 weeks (or earlier for those who discontinue study therapy)
 - Maximum change (rise or fall) in bone-ALP during the treatment period reported for each patient as a waterfall plot
- Changes in total-ALP will be defined as for bone-ALP above
- PSA decline will be reported on all patients. Using PCWG2 guidelines ¹, the percentage of change in PSA from baseline to 12 weeks, as well as the maximum decline in PSA will be reported for each patient using a waterfall plot.
- Progression, for those patients showing an initial decline in PSA from baseline, is defined as an increase in PSA that is $\geq 25\%$ and ≥ 2 ng/mL above the nadir, and which is confirmed by a second value 3 or more weeks later (i.e., a confirmed rising trend).
- Progression, for those patients with no decline in PSA from baseline, is defined as an increase in PSA that is $\geq 25\%$ and ≥ 2 ng/mL after 12 weeks. Note: PSA progression as such will not lead to study discontinuation
- Time to First Radiographic or Clinical Progression (TTFROCP) based on RECIST version 1.1 and Prostate Cancer Working Group 2 (PCWG2) definitions
- Changes in other bone markers:
 - Serum C-telopeptide (sCTX-1)
 - N-terminal propeptide of procollagen type 1 (PINP)
- Radiographic response through the RECIST criteria 1.1 will also be determined using FDG PET/CT to assess for treatment effect in bone.
- Time to pain progression, defined as time until a ≥ 2 point increase in pain compared to baseline confirmed at least 4 weeks later.
- Change in analgesic use assessed by the WHO analgesic ladder
- Changes in measure of tiredness measured by the worst fatigue item (item #3) from the Brief Fatigue Inventory.
- Measures of pain interference specifically evaluating its affect on general activity and sleep as assessed on BPI
- Evaluate the short and long term toxicity to treatment

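### Long-term toxicity is a secondary endpoint, but the plan conflicts on whether new non-serious adverse events are collected beyond 4 weeks after the last dose, and no adverse-event summary clearly covers follow-up

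*Combined protocol and SAP*

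**What the plan says.** **Endpoint.** The synopsis and section 8.2 list, among the secondary endpoints, "Evaluate the short and long term toxicity to treatment". Footnote e to the schedule in section 5 says that patients at the three-monthly follow-up visits are to "be assessed for any potential long term toxicity as well as key efficacy parameters".

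**Follow-up visits.** Section 5.3 continues them "until 6 months after the safety follow-up visit for a total of 2 visits or until initiation of another therapy". It then gives a list under the words "The following assessments will be performed at these visits": performance status, pain and fatigue scales, analgesic diary, blood tests (including hematology and biochemistry) and imaging. Adverse events are not on it. The corresponding lists for the treatment period (5.2) and the safety visit (5.2.1) each have an adverse-event line.

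**Collection window.** Section 5.4 opens with "Patients will be closely monitored throughout the study for adverse events, at least every four weeks". The same paragraph then sets monitoring from the first dose "through 4 weeks following the last administration or until all study drug-related toxicities resolve, stabilize, return to baseline or are deemed irreversible", with the longer of the two limits applying. Section 5.5 first requires adverse events of every grade to be evaluated at each visit while the patient is in the study, then gives a window of about 4 weeks for patients who have left the treatment phase. Section 7.1.1 says: "An adverse event is any untoward medical occurrence in a research patient during a clinical study or within 4 weeks post treatment". Section 7.1.2 requires serious events after 4 weeks to be recorded if a causal link is suspected.

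**Analysis.** Section 10.1.2 tabulates adverse events before and during treatment. Section 10.3.1 summarizes treatment-emergent events. Neither describes a summary for the follow-up period.

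**The concern.** The protocol itself gives reasons to look for late toxicity. Section 1.3.1 warns of bone marrow changes and new primary cancers in the longer term. Section 1.2.1 reports bone marrow failure or ongoing pancytopenia in 2% of treated patients in the phase III trial, against none on placebo, with two deaths from marrow failure.

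If the text does not settle whether new events are recorded at follow-up, three sites may settle it differently. A new non-serious cytopenia on a planned follow-up blood test could be an adverse event at one site and only a laboratory value at another. If the adverse-event tables stop near the end of treatment, such an event may not appear in them even where it was recorded. A report of little or no late toxicity could then partly reflect what was collected and tabulated. Events not recorded at the time are hard to recover later.

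**Working it through.** The plan gives no figure for this point, so the check is visit timing followed by a reading of the passages side by side.

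**1. Where the follow-up visits fall.** Inputs: last dose at week 21 and safety visit at week 25 (section 5 schedule); follow-up visits 3 and 6 months after the safety visit (5.3); 30.44 days per month.

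- Safety visit: 25 − 21 = 4 weeks after the last dose.
- Three months: 3 × 30.44 / 7 = 13.0 weeks.
- First follow-up visit: 4 + 13 = 17 weeks after the last dose.
- Second follow-up visit: 4 + 26 = 30 weeks, or 30.1 × 7 / 30.44 = 6.9 months.
- With the permitted windows (safety visit up to 7 days early, follow-up visit up to 1 week early), the first visit is no earlier than 3 + 13 − 1 = 15 weeks.

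Both follow-up visits therefore lie well past the 4-week mark, and the choice of governing rule decides what is recorded at them.

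**2. Is a new event recorded?** Take a new, non-serious fall in platelets first seen at the 17-week visit.

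| Place | Recorded as an adverse event? |
|---|---|
| Schedule footnote e | Yes: late toxicity is to be assessed at this visit |
| 5.5, first sentence | Yes: every grade, every visit |
| 5.4, opening sentence | Yes on its wording, although three-monthly visits cannot meet its four-weekly frequency |
| 5.4, window | No: past 4 weeks, and the extension is for drug-related toxicities still unresolved |
| 5.5, second sentence | No, for the same reason, in patients discontinued from treatment |
| 5.3 list | No adverse-event item, though hematology is drawn |
| 7.1.1 | Either: 4 weeks is one limb, and the other is the duration of the study |
| 7.1.2 | Not required: the event is not serious |
| 7.2.1 | Yes if clinically significant; no time limit of its own |

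The passages do not give one answer.

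**3. Is it tabulated if recorded?**

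- 10.1.2 stops at the end of treatment. The synopsis ends the treatment period 4 weeks after the last administration, so the event at 17 weeks falls outside.
- 10.3.1 is limited to treatment-emergent events. The term is not defined by a time window and no follow-up table is described.
- 10.3.2 summarizes serious events and those leading to withdrawal or death, without a time window. A late serious event could enter, but would not be shown as late.
- 10.3.3 promises selected laboratory parameters, again without a time frame.

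No adverse-event summary clearly includes the event.

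**The case against.** A reader might infer that routine collection simply ends at 4 weeks and that long-term toxicity cannot be evaluated from the planned data. The documents do not support that, for these reasons:

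- Footnote e is an instruction attached to the follow-up visits, and the first sentence of 5.5 covers every visit during participation.
- Section 7.1.1 joins its two limbs with an or. The synopsis ends the study at the last patient's last follow-up visit, so those visits can count as part of the study.
- Four weeks is a minimum in 5.4, because the later of the two limits applies.
- Hematology and biochemistry are drawn at both visits. Section 7.2.1 sends clinically significant results to the adverse-event record, and 10.3.3 offers a laboratory summary.
- Suspected-related late serious events have no end date (7.1.2). Section 7.1.8 lets blood dyscrasias without hospital admission count as serious. A second cancer may be a reason for withdrawal, which goes in the CRF (5.6.1).
- Section 10.2.2 gives a start to safety evaluability and no end.

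All of this stands against the stronger reading. For the same reason, the 4-week window should not be expressed as a share of post-treatment observation: that presumes the narrowest rule governs, which is the question left open.

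Three things remain after the objection. Extending follow-up of an unresolved toxicity does not clearly open collection of new ones. The 5.3 list omits an item that the two preceding visit lists contain. Neither 10.1.2 nor 10.3.1 clearly reaches past treatment.

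The available text of the schedule does not show where the adverse-event bar ends. If it reaches the follow-up column, that adds one statement in favour of collection but leaves 5.3 and the analysis sections unchanged.

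**Conclusion.** The point holds as an internal inconsistency with a gap in the analysis plan. The plan conflicts on the collection of new non-serious adverse events that start more than 4 weeks after the last dose, and no planned adverse-event summary clearly covers the follow-up period in which the endpoint is to be assessed. Both follow-up visits are affected. Part of the endpoint remains reportable from suspected-related late serious events and follow-up laboratory data.

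The timing assumes six doses on the nominal schedule; follow-up is shorter if another therapy starts. Even with the text repaired, observation reaches only about 7 months after the last dose. Section 1.3.1 places new cancers and marrow changes over several years, and this trial cannot address risks on that scale. The priority is moderate: this is a secondary endpoint and the repair is cheap.

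**What to change.** 1. Reconcile 5.4, 5.5 and 7.1.1 with footnote e, so that one rule states whether and until when new adverse events are recorded after the 4-week window.
2. Add to the 5.3 list an adverse-event item covering drug-related events, new cytopenias on the hematology already planned, and new malignancies.
3. Add to 10.1.2 and 10.3.1 a separate table of events starting more than 4 weeks after the last dose.
4. State that these data cover at most about 7 months after the last dose and do not address risks arising over several years.

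The cost is one CRF page at visits that already take place, and one table. No extra visit or blood test is needed.

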5.5 Dosing Delays and Dose Modifications for Toxicities

At each study visit for the duration of their participation in the study, patients will be evaluated for adverse events (all grades), serious adverse events (SAEs), and adverse events that require study drug interruption or discontinuation. Patients discontinued from the treatment phase of the study for any reason will be followed for toxicity until approximately 4 weeks after the last dose of the study drug or until all study drug-related toxicities resolve, stabilize, return to baseline or are deemed irreversible, whichever is longer.

Every effort should be made to administer the full dosing regimen of Ra-223 dichloride. Adjustment of dose level is not permitted.

Study visits during the treatment period should occur at 4 weeks intervals (within a window of +/- 7 days). Dosing delays may be instituted under the following circumstances:

Disease progression

The Investigator should delay cytotoxic chemotherapy, other systemic radioisotope, hemibody external radiotherapy or other investigational drug until the follow-up period. If such treatments have to be given during the treatment period, further study drug administrations must be discontinued. Patients may be on other non-chemotherapy anti-cancer treatments, per FDA labeling of Radium-223, provided that these are not changed during the period of pain assessments.

Radium-223

MSKCC

PCCTC LOI: c13-124

IRB#: 14-098 A (5)

Patients with a rising PSA should not be considered to have progressive disease, as a rising PSA does not imply lack of clinical benefit with treatment radium-223.

Patients with radiographic progression are not required to discontinue treatment or to be defined for this trial as having disease progression, as there are no known data associating such radiographic findings with a lack of clinical benefit with radium 223.

Patients with unequivocal clinical progression should be considered treatment failures, and treatment under the auspices of the protocol will be discontinued.

Myelosuppression

If a patient experiences Common Terminology Criteria for Adverse Events¹ (CTCAE) grade 3-4 neutropenia or thrombocytopenia lasting > 14 days, further study drug administrations must be discontinued.

If a patient experiences CTCAE grade 3-4 neutropenia the study drug administration should be delayed until recovery to grade 2 (minimum $1.0 \times 10^9 / \text{L}$) or better.

In case of thrombocytopenia grade 3-4 the study drug administration should be delayed until recovery to CTCAE grade 2 (minimum $50 \times 10^9 / \text{L}$) or better.

In case of hemoglobin CTCAE grade 3-4, the value needs to recover to CTCAE grade 2 (minimum 8.0 g/dL) or better before next study drug administration. Blood transfusion is acceptable between study drug administrations.

Gastrointestinal events:

Diarrhea:

No prophylactic treatment for diarrhea is recommended. Antidiarrheals can be used when needed. A further dose of study medication should not be given before recovered to CTCAE grade 2 or baseline.

Nausea/Vomiting:

No prophylactic treatments for nausea or vomiting are recommended, but anti-emetic drugs can be used when needed. A further dose of study medication should not be given before recovered to CTCAE grade 2 or baseline.

Constipation:

Patients can continue laxative as concomitant medication, but start of prophylactic treatments before study drug injection are not recommended. Laxative can be used when needed. A further dose of study medication should not be given before recovered to CTCAE grade 2 or baseline.

Spinal Cord Compression

¹ Common Terminology Criteria for Adverse Events, Version 4.0 (CTC AE); Published May 28, 2009

Radium-223

MSKCC

PCCTC LOI: c13-124

IRB#: 14-098 A (5)

Patients, who experience spinal cord compression and require treatment with XRT in the treatment period prior to week 8, will be taken off-study and declared non-evaluable.

Surgical Intervention

If surgery is required, the patient should continue with study treatment, if this is considered safe in the treating Investigator's opinion. The surgeon needs to be notified that the patient has been given radioactive drug, and needs to follow the guidelines for radioactive protection.

Any Other Toxicity

If a patient experiences any non-hematological grade CTCAE grade 4 toxicity lasting > 7 days despite adequate treatment, further study drug administration must be discontinued.

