10. STATISTICAL CONSIDERATIONS

10.1 Study Endpoints

10.1.1 *Analysis of the primary endpoint*

The primary objective of this phase II study is to determine the effect of Radium-223 on pain improvement for patients with symptomatic metastatic castration-resistant disease. The primary endpoint of the study is a 30% decline in the BPI worst pain item from baseline to week 8, with a confirmed reduction at week 12 without an escalation of the subject's pain regimen from Step 1 to Step 2 or Step 2 to Step 3 of the WHO analgesic ladder. The baseline BPI worst pain score average will be based on the worst pain scores completed by the patient in the 7 consecutive pretreatment days. A minimum of 4 days of pain scores must be completed by the patient in the 7

day window in order to calculate the average worst pain score. We define this event as a response and propose declaring the treatment effective if the probability of a response in the population exceeds 0.20.

A maximum of 63 patients will be entered onto the study. A two-stage design that differentiates between response rates of 0.20 and 0.35 will be used to assess treatment efficacy. In the first stage of the study 27 patients will be enrolled. If at most 5 patients respond, accrual will be terminated. If at least 6 patients respond, an additional 36 patients will be entered onto the study. At the conclusion of this second stage, if at least 17/63 patients respond, the treatment will be declared effective. The probability of declaring the treatment effective is 0.10 when the response rate in the population is 0.20 and increases to 0.90 when the response rate is 0.35.

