10.2 Analysis Populations

10.2.1 *Evaluable population*

Responders will be defined by a 30% decline in the BPI worst pain item from baseline to week 8, with a confirmed reduction at week 12 without an escalation of the subject's pain regimen from Step 1 to Step 2 or Step 2 to Step 3 of the WHO analgesic ladder.

Patients with progressive pain will be defined by time until a ≥ 2 point increase in the average "worst pain" item on the BPI over a 7 day period compared to baseline is seen and confirmed at least 2 weeks later.

Patients who are neither categorized as pain responders or are categorized as ones with progressive pain will be recorded as non-responders.

All patients who meet eligibility criteria and receive at least 1 dose of study medication will be included in the main analysis of the response rate, even if there are major protocol deviations (e.g., incorrect treatment schedule or drug administration). Each patient will be assigned to one of the above categories.

10.2.2 *Safety population*

All patients enrolled in the study will be included in the safety analysis population and considered evaluable for toxicity and safety from the time of their first dose. Demographic and baseline characteristics for the safety population will be summarized by number and percent for categorical data (e.g., sex, race/ethnicity) and by descriptive statistics for continuous data (e.g., weight, vital signs, EKG readings, disease status).

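### The responder rule disqualifies only a WHO-step increase, so a patient given focal radiotherapy or changed anti-cancer therapy before the week-12 assessment can be counted as a radium-223 pain responder

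*Combined protocol and SAP*

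**What the plan says.** **Endpoint.** Sections 8.1, 10.1.1 and 10.2.1 define response in the same way: a 30% decline in BPI worst pain from baseline to week 8, confirmed at week 12, with no move from WHO Step 1 to 2 or from Step 2 to 3. No other treatment is named as forfeiting response.

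**Analysis set.** Under 10.2.1, every eligible patient with at least one dose "will be included in the main analysis of the response rate, even if there are major protocol deviations". Each is placed in one of three categories: responder, progressive pain or non-responder.

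**Co-interventions during treatment.** Section 5.5 states: "The Investigator should delay cytotoxic chemotherapy, other systemic radioisotope, hemibody external radiotherapy or other investigational drug until the follow-up period". If any of these has to be given, further study drug is stopped. Focal external-beam radiotherapy is not mentioned. Sections 3.3, 5.2, 5.5 and 5.7 allow other non-chemotherapy anti-cancer treatment only if it is not changed during the pain assessments. Under 5.6.1, withdrawal for non-protocol anti-cancer therapy is optional.

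**The one radiotherapy case addressed.** Section 5.5 says that patients with spinal cord compression who "require treatment with XRT in the treatment period prior to week 8, will be taken off-study and declared non-evaluable". Section 5.6.1 replaces withdrawn patients unless they are evaluable under 10.2.1.

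**Design.** Section 10.1.1 sets out a two-stage rule that "differentiates between response rates of 0.20 and 0.35".

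**The concern.** Focal radiotherapy to a painful bone site, or a new or altered anti-cancer drug, can itself lower the worst-pain score. The protocol recognises this: it excludes external-beam radiotherapy and new anti-cancer agents within 4 weeks before registration (3.3), and it bars changes to background therapy while pain is being measured. These are rules about entry and conduct. None of them reaches the definition of a responder, so the plan does not say how a patient is scored once such an event has happened.

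The trial has one arm, so no control group absorbs relief from other treatments. The decision is a count against a fixed threshold of 17 responders, which makes it sensitive to a few misattributed responses.

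**Working it through.** **Inputs from 10.1.1.** Stage 1: "In the first stage of the study 27 patients will be enrolled. If at most 5 patients respond, accrual will be terminated". Stage 2: "if at least 17/63 patients respond, the treatment will be declared effective", which means 36 further patients. Stated properties: "The probability of declaring the treatment effective is 0.10 when the response rate in the population is 0.20", and this "increases to 0.90 when the response rate is 0.35".

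**Step 1: reproduce the design.** For a counted response rate p,

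P(effective) = Σ over x = 6 to 27 of P(X₁ = x; 27, p) × P(X₂ ≥ 17 − x; 36, p).

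This gives 0.0999 at p = 0.20 and 0.902 at p = 0.35. Both stated figures are confirmed; the design arithmetic is not in error.

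**Step 2: effect of misattributed responses.** The documents give neither the frequency nor the effect of co-interventions, so both are assumed. Let f be the share of patients affected before the week-12 assessment (5-10%) and s the chance that the pain criterion is met because of the co-intervention (40-60%). The true radium-223 response rate is 0.20. There are two ways to combine them:

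- A: a fraction s of all affected patients meets the criterion. Counted rate = (1 − f) × 0.20 + f × s.
- B: extra responses arise only among affected patients who would not have responded to radium-223. Counted rate = 0.20 + 0.80 × f × s.

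| f | s | Rate, A | P(effective), A | Rate, B | P(effective), B |
|---|---|---|---|---|---|
| 5% | 40% | 0.190 + 0.020 = 0.210 | 0.140 | 0.20 + 0.016 = 0.216 | 0.167 |
| 5% | 60% | 0.190 + 0.030 = 0.220 | 0.187 | 0.20 + 0.024 = 0.224 | 0.209 |
| 10% | 40% | 0.180 + 0.040 = 0.220 | 0.187 | 0.20 + 0.032 = 0.232 | 0.254 |
| 10% | 60% | 0.180 + 0.060 = 0.240 | 0.304 | 0.20 + 0.048 = 0.248 | 0.357 |

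Across both, the counted rate is 0.21-0.25 and the chance of declaring efficacy 0.14-0.36, against a nominal 0.10.

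**Step 3: effect of scoring the events as non-response.** If the events occur regardless of response, the counted rate is p × (1 − f).

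| f | True 0.20 becomes | P(effective) | True 0.35 becomes | P(effective) |
|---|---|---|---|---|
| 5% | 0.190 | 0.069 | 0.3325 | 0.849 |
| 10% | 0.180 | 0.045 | 0.315 | 0.776 |

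**Step 4: the provisions side by side.** Section 10.2.1 keeps every eligible dosed patient. Section 5.5 declares an eligible dosed patient non-evaluable if irradiated for cord compression before week 8. Section 5.6.1 makes replacement depend on evaluability under 10.2.1, so its result depends on which section governs. Radiotherapy for cord compression between weeks 8 and 12 is not addressed. Sections 5.2 and 5.5 also use a treatment-failure label that 10.2.1 does not. The confirmed 2-point pain rise in 5.2 corresponds in substance to 10.2.1's progressive-pain category, but unequivocal clinical progression in 5.5 has no counterpart there.

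**The case against.** Much of the affected group is already constrained. Unequivocal clinical progression is a treatment failure (5.5), symptomatic progression is a ground for removal (5.6), and a confirmed 2-point pain rise takes the patient off trial (5.2). Changing background therapy is prohibited, so that route arises only as a deviation. Responses are subject to committee review (9.2.1). Keeping deviators in the main analysis is a legitimate choice. All of this stands and limits how many patients are affected. It does not close the gap: a prohibition does not say how a breach is scored, clinical failure is not tied to the 10.2.1 categories, focal radiotherapy need not follow unequivocal progression, and 9.2.1 gives the committee no scoring rule for these events.

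Three stronger readings are tempting, and the documents do not support them.

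- *Every such patient is counted as a responder.* The week-8 decline and week-12 confirmation must still be met without a step increase. Radiotherapy after week 8 cannot create the week-8 decline; at most it helps the confirmation.
- *Cord-compression patients leave the denominator and so inflate the rate.* That is one side of the conflict between 5.5 and 10.2.1; on the wording of 10.2.1 they stay in.
- *The false-positive chance reaches 0.44.* That needs a counted rate of 0.20 + 0.10 × 0.60 = 0.26, which assumes that every affected patient would otherwise have been a radium-223 non-responder. Nothing in the documents supports that.

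**Conclusion.** The concern holds in this form: as written, the plan can credit relief from focal radiotherapy, or from a prohibited change of anti-cancer therapy, to radium-223, and its sections disagree on whether one group of irradiated patients is analysed at all. The gap in the responder rule and the conflict between 5.5 and 10.2.1 follow from the text and need no assumption.

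The size does rest on assumption. With 5-10% of patients affected and 40-60% of those meeting the criterion, a true 0.20 is counted as about 0.21-0.25 and the chance of declaring efficacy rises from 0.10 to about 0.14-0.36. If such events are rarer, the effect is smaller. Even so, two percentage points of misattributed response (0.20 to 0.22) raise the error from 0.10 to 0.19. This should be corrected, although the stated design properties are right for the rule as given.

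**What to change.** The change concerns scoring only and does not alter which treatments patients may receive.

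1. In 8.1, 10.1.1 and 10.2.1, state that radiotherapy to bone, or new or changed systemic anti-cancer therapy, from first dose to the end of the week-12 pain window counts as non-response, with the patient kept in the denominator. The window should start at first dose, not at run-in: registration is completed after run-in, and radiotherapy or a new agent in the 4 weeks before registration already makes a patient ineligible under 3.3.
2. Reconcile the non-evaluable sentence in 5.5 and the replacement rule in 5.6.1 with 10.2.1.
3. Map treatment failure in 5.2 and 5.5 to non-response for the primary endpoint.
4. Confirm that on-study radiotherapy is captured on the CRF. The schedule lists concomitant medications and 5.7 says that concomitant prostate-cancer treatments are recorded, but neither names radiotherapy.
5. Report the responder count ignoring these events as a sensitivity analysis.

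The text change is small. The statistical cost is not negligible: if the events are unrelated to response, power at 0.35 falls from 0.90 to about 0.85 with 5% affected and about 0.78 with 10%. The sponsor should weigh this against the protection of the 0.10 error rate.
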